- a. Proportion of patients with a new grade 3 or 4 adverse event.
- b. Proportion of patients with acute cellular rejection during fenofibrate treatment
- c. Mean change in calculated glomerular filtration rate (eGFR) from baseline during fenofibrate treatment weeks 4, 8, 12, and at 4 weeks after end of treatment
- d. Proportion of patients with myopathy confirmed by serum creatine kinase elevation at weeks 4, 8, 12, and at 4 weeks after end of treatment

The FICsDCD Study

Specific Aim 2: To assess IC incidence after 12 weeks of once-daily fenofibrate (Lofibra) in DCD LT recipients, compared with a historical, untreated control. Treatment and control populations will have an elevated predicted risk of IC, defined as alkaline phosphatase >2.5x upper limit of normal (ULN) at 21-60 days after LT.

Primary endpoint: IC incidence with 12 weeks fenofibrate versus a historical untreated cohort.

Secondary endpoints:

- a. Incidence of any IC-related complication at 12 weeks of fenofibrate treatment as a composite endpoint: biliary intervention (biliary stricture dilation, endoscopic biliary stent placement, percutaneous biliary drain placement), initiation of antimicrobial therapy for cholangitis or biloma, re-transplant evaluation due to IC, or death attributed to IC.
- b. Rate of alkaline phosphatase improvement to <1.67x ULN after 12 weeks fenofibrate.

Specific Aim 3: To assess the association between serum biomarkers and IC development.

Endpoints: Correlation of serum alkaline phosphatase, gamma glutamyl transferase, bile acids, fibroblast growth factor 19 (FGF19) and 7-alpha-hydroxy-4-cholesten-3-one (7AC4) levels at weeks 0, 4, 8, and 12 of treatment, with development of IC at 12 weeks of treatment.

II. Background and Significance

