While approved for dyslipidemia and used off-label for pre-LT PBC and PSC, fibrate safety or efficacy have not been studied in any transplant population for any indication. Additionally, despite the likely benefits (including cost of \$5-25/month), the known risk profile of fibrates, including nephrotoxicity, hepatotoxicity, and myotoxicity, require study in LT recipients who are prone to these toxicities from immunosuppressives and/or their baseline clinical state.

In this prospective pilot study, our primary aim is to describe the tolerability and safety of 12 weeks of once-daily fenofibrate in a LT population, with efficacy as a secondary aim, and determining associations of cholestasis and bile acid activity biomarkers with IC as a tertiary aim.

We believe this pilot study to have at least four key implications on current post-LT care or in opening new areas of investigation. First, demonstrating fenofibrate tolerability and safety early after LT is useful context of IC but also because both PBC and PSC have a 20% recurrence rate after LT and fenofibrate may be considered for post-LT prophylaxis (current standard of care is universal lifelong ursodeoxycholic acid after LT for PBC, and observation alone after LT for PSC). Second, if an efficacy signal is demonstrated, we will leverage the existing three-site Mayo Clinic collaboration (together the largest transplant consortium by far) to conduct a randomized controlled trial to more conclusively assess efficacy of fenofibrate in preventing IC. Third, we hope to determine if biomarkers besides ALP—a test confounded by other liver processes—are associated with IC and facilitate early detection. Fourth, data gathered may allow us to investigate a predictive scoring model utilizing donor and patient characteristics and these biomarkers.

The FICsDCD Study

III. Progress Report and Preliminary Studies

As two of the largest DCD LT program in the nation, the MCA and MCF transplant hepatology teams including this study's PI and Co-Is are experienced in diagnosing and managing IC. Our group holds a monthly DCD IC Multidisciplinary Conference to review cases and discuss management. Finally, the MCA LT Program has contributed to seminal peer-reviewed papers on the DCD IC syndrome including the recently proposed IC classification system.¹ At present we are developing a dataset of over 300 DCD LT recipients at our center which will be used to identify the historical controls of this study.

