IV. Research Design and Methods

Study design: A single-arm, open-label, prospective study of 12 weeks of fenofibrate (Lofibra) 160mg once daily in donation after circulatory death liver transplant recipients who have serum alkaline phosphatase $>2.5 \times$ ULN 21-60 days after transplantation, to determine fenofibrate tolerability, safety, and efficacy in preventing the ischemic cholangiopathy.

Treatment cohort: Recipients of DCD liver transplants at MCA or MCF

Historical cohort: DCD liver transplant recipients at MCA or MCF between 1/1/2016-6/1/2021

Diagnosis of IC: We will utilize previously-published diagnostic criteria for IC, defined as the occurrence of non-anastomotic biliary strictures in the absence of hepatic artery compromise¹

Inclusion criteria:

1. Female or male patients who have undergone DCD LT
2. At least one serum ALP level $>2.5 \times$ ULN between post-LT days 21-60 days (inclusive) after LT.

Exclusion criteria:

1. LT performed for primary sclerosing cholangitis or primary biliary cholangitis
2. Hepatic artery compromise (e.g thrombosis, stenosis), evaluated on abdominal doppler ultrasonography or angiography prior to enrollment..
3. Untreated biliary anastomotic (surgical) stricture or bile leak between days 0-60 after LT, evaluated during routine clinic examinations, labs, and abdominal ultrasonography.
4. Baseline GFR <30 ml/min
5. Previously known intolerance or allergy to fenofibrate
6. Other clinically significant comorbid condition, including psychiatric conditions, which in the opinion of the study team, may interfere with patient treatment, safety, assessment, or compliance with the treatment
7. Adults lacking capacity to consent to treatment

Interventions:

1. Consenting eligible patients will receive the fenofibrate formulation *Lofibra*, 160mg or renally-adjusted equivalent daily. Intended treatment duration of 12 weeks.
2. Post-transplant laboratory monitoring will be per standard Institutional protocol, at least weekly, through treatment period. Study laboratory monitoring will be done as below.

Analyses:

Specific Aim1:

- a. Tolerability: Proportion of patients who discontinue fenofibrate due to adverse event.
- b. Safety:
 - Proportion of patients with a new grade 3 or 4 adverse events based on CTCAE 5.0 Scale

The FICsDCD Study

- Proportion of patients with acute cellular rejection during fenofibrate treatment
- Mean change in eGFR from baseline at treatment weeks 4, 8, 12, and post-treatment week 4

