- Proportion of patients with elevated serum CK at weeks 4, 8, 12, and post-treatment week 4

Specific Aim 2:

- a. Efficacy: We will use a two-group design to test whether Group 1 (treatment) proportion (P1) is different from Group 2 (control) proportion (P2) ($H_0: P_1 - P_2 = 0$ versus $H_1: P_1 - P_2 \neq 0$). We will use a two-sided, two-sample Fisher's Exact Test with Type I error rate (α) of 0.05.
- b. Sample size: Allowing a 10% dropout rate, a sample size of 32 in the treatment arm and 116 in the historical control arm (1:4 ratio) will achieve 80% power to detect an IC proportion reduction of 30% in the control arm to 5% in the treatment arm.

Specific Aim 3: Serum biomarker association with IC development: We will use the Wilcoxon Rank-Sum test to compare serum ALP, gamma glutamyl transferase, serum BA, FGF19 and 7AC4 levels at weeks 0, 4, 8, and 12 of treatment, with development of IC at 12 of treatment.

Data management: The study will use REDCap, a secure web platform for building and managing online databases and surveys for electronic data collection. REDCap provides automated export procedures for seamless data downloads to Excel and common statistical packages (SPSS, SAS, Stata, R), as well as a built-in project calendar, a scheduling module, ad hoc reporting tools, branching logic, file uploading, and calculated fields.

Schedule of Events

Procedure	Screening: Post-LT day 21-60	Treatment			Post Treatment
		Weeks 0-4	Weeks 5-8	Weeks 9-12	Week 4
Informed consent	X				
Inclusion and exclusion criteria	X				
Physical examination	X				
Medical history	X				
Intervention: fenofibrate		Daily	Daily	Daily	
Routine Labs*	X	Weekly	Weekly	Weekly	Weekly
Study Labs**	X	Once ^{a,b}	Week 6 ^b	Week 12 ^b	Once ^b
Lab result review		Weekly	Weekly	Weekly	Once
Assess tolerability, safety		Weekly	Once	Once	Once

*Protocol transplant monitoring labs (billed to insurance): total bilirubin, ALP, alanine aminotransferase, aspartate aminotransferase, sodium, potassium, creatinine, eGFR, and complete blood count.

**Study labs per FICsDCD budget: GGT, serum bile acids, CK, FGF19 (ELISA), 7AC4 (LC-MS)

^a collect within 3 days after start of treatment

^b combine with transplant monitoring labs

Study Strengths and Limitations:

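### CK, GGT, bile acids, FGF19 and 7AC4 are to be analysed at weeks 4 and 8, but the Schedule of Events samples them at week 6 and at neither of those weeks

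*Combined protocol and SAP*

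**What the plan says.** **Endpoints.** In section I (Specific Aims), secondary endpoint d of Aim 1 is "Proportion of patients with myopathy confirmed by serum creatine kinase elevation at weeks 4, 8, 12, and at 4 weeks after end of treatment". Aim 3 relates ALP, GGT, bile acids, FGF19 and 7AC4 to ischemic cholangiopathy (IC), using "levels at weeks 0, 4, 8, and 12 of treatment, with development of IC at 12 weeks of treatment".

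**Analyses.** Section IV repeats both lists. The Aim 1 safety analyses give the same four CK times, and the Aim 3 analysis applies the Wilcoxon rank-sum test to ALP, GGT and "serum BA, FGF19 and 7AC4 levels at weeks 0, 4, 8, and 12 of treatment".

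**Sampling.** Item 2 under Interventions (section IV) hands study-laboratory timing to the schedule: "Study laboratory monitoring will be done as below". The Study Labs row of the Schedule of Events has five entries: screening, once in weeks 0-4, week 6, week 12, and once in the post-treatment week 4 column. Footnote a fixes the weeks 0-4 sample: "collect within 3 days after start of treatment". Footnote b combines the study samples after screening with transplant monitoring labs.

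**Panels.** The study panel is "Study labs per FICsDCD budget: GGT, serum bile acids, CK, FGF19 (ELISA), 7AC4 (LC-MS)". The routine panel, run weekly during treatment, is "total bilirubin, ALP, alanine aminotransferase, aspartate aminotransferase, sodium, potassium, creatinine, eGFR, and complete blood count".

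**Rank of the aims.** Section II makes tolerability and safety the primary aim and describes "determining associations of cholestasis and bile acid activity biomarkers with IC as a tertiary aim".

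**The concern.** The endpoint text and the sampling schedule cannot both be followed. Five analytes are to be reported at weeks 4 and 8 but are not measured then, and they are measured at week 6, a time no endpoint names. Week 6 lies two weeks from each of the named weeks, and the plan has no visit-window rule that assigns it to either. Site staff and the analyst would have to leave the named times empty, sample off schedule, or decide later what the week-6 value stands for.

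Two things are at stake:

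- **Safety.** Section V (Protection) lists myotoxicity among the particular areas of interest, and Aim 1d requires CK to confirm myopathy. The weekly labs that section V relies on for monitoring contain no CK.
- **Biomarkers.** Section II hopes to find markers other than ALP that help early detection. ALP is the only Aim 3 marker sampled at every named week. All the others lack both intermediate on-treatment times.

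**Working it through.** The plan gives no figure to reproduce. The check sets each named time against the schedule and counts the gaps.

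**Inputs**
- Times named: Aim 1d, Aim 3 and the Analyses.
- Times sampled: Study Labs and Routine Labs rows of the Schedule of Events, with footnotes a and b.
- Panel contents: the two laboratory footnotes.
- Treated patients: 32 (section V, Population).

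**Named times against scheduled times**

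| Analyte | Named times | Panel | Named times with no scheduled measurement |
|---|---|---|---|
| CK | 4, 8, 12, post-treatment 4 | Study | 4, 8 |
| GGT | 0, 4, 8, 12 | Study | 4, 8 |
| Bile acids | 0, 4, 8, 12 | Study | 4, 8 |
| FGF19 | 0, 4, 8, 12 | Study | 4, 8 |
| 7AC4 | 0, 4, 8, 12 | Study | 4, 8 |
| ALP | 0, 4, 8, 12 | Routine, weekly | none |
| eGFR (Aim 1c) | 4, 8, 12, post-treatment 4 | Routine, weekly | none |

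**Counts**
- CK: 2 of 4 named times are empty. At 32 patients that is 2 × 32 = 64 of 4 × 32 = 128 values.
- Aim 3: 5 markers × 4 weeks = 20 comparisons. Empty: 4 markers × 2 weeks = 8. Remaining: ALP 4 + (4 markers × 2 weeks) = 12. In values, 8 × 32 = 256 of 20 × 32 = 640.
- Both together: 5 analytes × 2 weeks = 10 analyte-by-week cells with no measurement.

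**Allowing for dropout.** The sample-size paragraph allows 10%, and 32 × 0.9 = 28.8, about 29 patients. The counts become 2 × 29 = 58 of 116 for CK and 8 × 29 = 232 of 580 for Aim 3. The fractions do not change.

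**Other readings**
- *The weeks 0-4 sample is really week 4.* Footnote a rules this out. Even on that reading week 8 stays empty, leaving 1 of 4 CK times and 4 of 20 comparisons without data.
- *Week 6 is a table-reading fault.* The row has five entries for five columns, week 6 falls within the weeks 5-8 column, and week 12 falls within weeks 9-12.
- *Another section supplies the samples.* Section V says blood will be collected, analysed and biobanked, but gives no times and no analytes.

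**The case against.** The mismatch is not in dispute; the case against concerns how much it matters and how to put it right.

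**The Aim 3 loss may cost little.** Study samples come only from treated patients. With 29 evaluable and the protocol's target IC proportion of 5%, about 29 × 0.05 = 1.5 cases are expected. The chance of none or one is 0.95^29 + 29 × 0.05 × 0.95^28 = 0.226 + 0.345 = 0.57. With one case the smallest two-sided exact Wilcoxon p-value is 2/29 = 0.069; with none the test cannot be run. This has force only if the drug works as hoped. At 30%, about 29 × 0.30 = 8.7 cases are expected and the missing weeks matter. It does not touch the CK gap.

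**CK is not absent.** It is measured within 3 days of start, at weeks 6 and 12, and after treatment, and tolerability is assessed weekly in the first four weeks. That is true, but clinical assessment does not supply the CK confirmation that Aim 1d requires.

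**Blood is drawn at weeks 4 and 8 anyway.** What is missing is a scheduled assay of the five analytes rather than a venepuncture. This is correct and bears on cost. It does not rescue the endpoints, because nothing says that blood will be stored or assayed for them.

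**Week 0 is itself loosely defined.** Screening can fall anywhere from day 21 to day 60 after transplant, with no stated interval to first dose, and the other candidate may be taken after dosing has begun. No rule chooses between them. This stands, and any correction should settle it.

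**Conclusion.** The concern holds. As written, the plan leaves half of the named CK times (2 of 4) and 40% of the Aim 3 comparisons (8 of 20) with no scheduled measurement, and it collects a week-6 panel that no endpoint uses. This is a contradiction between two parts of the plan, each endpoint list being stated twice, and not merely a missing detail.

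Its reach is limited. The primary endpoints of Aims 1 and 2, ALP, eGFR, and the week-12 and post-treatment values are unaffected, and week 0 has a sample once the plan says which one it is. The CK gap is the more important half, because safety is the primary aim and myotoxicity is a stated interest.

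The conclusion assumes only that the Schedule of Events governs study samples, as Interventions item 2 says. The value counts assume all 32 patients complete; the fractions do not depend on that. It should be fixed before enrolment, when correction is cheap.

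**What to change.** Make the schedule and the endpoint text agree. Either option is acceptable, and each should name the sample that counts as week 0.

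**Option A: change the schedule.** Measure the study panel at week 0, weeks 4, 8 and 12, and post-treatment week 4, leaving Aims 1d and 3 as they are.
- If screening serves as week 0 and the within-3-days sample is dropped, this is 5 × 32 = 160 panels, the same as now. The price is a baseline not tied to the start of treatment, so a maximum interval from screening to first dose should be set.
- If both early samples are kept, it is 6 × 32 = 192 panels, 32 more (32/160 = 20%).
- Weeks 4 and 8 coincide with weekly routine labs, so the extra cost is assays and not visits. The documents give no unit cost.

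**Option B: change the wording.** Keep the schedule and restate Aim 1d, Aim 3 and the Analyses as CK at week 6, week 12 and post-treatment week 4, and GGT, bile acids, FGF19 and 7AC4 at weeks 0, 6 and 12. With ALP kept at its four weeks, Aim 3 has 4 + (4 × 3) = 16 comparisons, all with a scheduled measurement. No panels are added. This accepts that no CK is scheduled between about day 3 and week 6.

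If early detection of muscle injury is a priority, Option A is the better choice, since it brings the first on-treatment check after the start forward to week 4.

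### Aim 2 sets no common day 0 and no common end of follow-up for counting IC in treated patients and historical controls, so controls can be observed longer

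*Combined protocol and SAP*

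**What the plan says.** **Treated patients.** Section I (Specific Aims) states Aim 2 as "To assess IC incidence after 12 weeks of once-daily fenofibrate (Lofibra) in DCD LT recipients, compared with a historical, untreated control". The primary endpoint is "Primary endpoint: IC incidence with 12 weeks fenofibrate versus a historical untreated cohort". Neither sentence says that IC is counted up to week 12. That is implied by the aim, by secondary endpoint (a), "Incidence of any IC-related complication at 12 weeks of fenofibrate treatment as a composite endpoint", and by Aim 3, which relates biomarkers "with development of IC at 12 weeks of treatment".

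**Controls.** Section IV gives "Historical cohort: DCD liver transplant recipients at MCA or MCF between 1/1/2016-6/1/2021". Aim 2 requires ALP above 2.5 times ULN at 21-60 days after transplant in both populations. Section V (Research Materials) plans an electronic record review of 32 participants and 116 controls and states no time limit. No section gives controls a day 0 or an end of IC ascertainment.

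**IC present at the start.** The IC definition in section IV is diagnostic only. The nearest exclusion is "Untreated biliary anastomotic (surgical) stricture or bile leak between days 0-60 after LT", which does not cover non-anastomotic strictures. No criterion requires freedom from IC at the start, in either group. The study design paragraph gives the purpose as "to determine fenofibrate tolerability, safety, and efficacy in preventing the ischemic cholangiopathy", but that is an aim and not an eligibility rule.

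**Analysis.** Section IV, Specific Aim 2, plans a two-sided Fisher's exact test at 0.05, with 32 treated and 116 controls, for 30% against 5% IC. Neither rate carries a time window.

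**The concern.** IC incidence is a cumulative quantity: it can only grow as patients are watched longer. A crude comparison of two proportions is fair only if both groups are counted from a comparable start over the same length of time. Here the treated group has an implied short window and the control group has none. If control records are read to their end, IC diagnosed after the treated window counts against the controls alone. The Fisher test has no censoring or time component and cannot correct for this.

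This is the plan's only between-group test of IC. Section II makes an efficacy signal, which is not defined numerically, the trigger for a randomized trial. The stake is therefore a possibly misleading go signal, not a treatment recommendation.

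**Working it through.** **1. The plan's own figure.** Inputs (section IV, Specific Aim 2): 5% and 30%, two-sided 0.05, 80% power, 1:4, 10% dropout.
- Pooled rate = (0.05 + 4 × 0.30)/5 = 0.25.
- n = [1.96 √(0.25 × 0.75 × 1.25) + 0.842 √(0.05 × 0.95 + 0.30 × 0.70/4)]² / 0.25² ≈ 23.6, so 24 treated.
- With continuity correction: (23.6/4) × [1 + √(1 + 10/(23.6 × 4 × 0.25))]² ≈ 28.4, so 29 treated and 4 × 29 = 116 controls.
- Dropout: 29 × 1.1 = 31.9, so 32.

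The stated sizes reproduce. Enumerating all tables, the exact Fisher power at 29 against 116 is 87.9%, so the sample size is not in dispute.

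**2. Observation time.**
- Treated: 21 + 84 = day 105 and 60 + 84 = day 144. This assumes dosing starts on days 21-60; no first-dose deadline is stated.
- Controls, to the protocol date of 28 October 2022: from 1 June 2021, 514 days = 16.9 months; from 1 January 2016, 2,492 days = 81.9 months.

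**3. False benefit from late control IC.** Let c be the control rate as counted, and f the share of that IC falling in the treated window. With no drug effect the treated rate is f × c. The false-benefit chance is the sum of binomial probabilities over all tables with two-sided Fisher p ≤ 0.05 and a lower treated proportion, at 29 against 116. The 30% is the planning rate. The 12% is the upper site rate for all DCD recipients (section II). The 20% is an intermediate assumption.

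| f | c = 30% | c = 20% | c = 12% |
|---|---|---|---|
| 1.0 (equal windows) | 1.7% | 1.6% | 1.2% |
| 0.9 | 3.4% | 2.7% | 1.8% |
| 0.8 | 6.5% | 4.5% | 2.6% |

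The documents do not give f. Section II places onset within weeks to months of transplant, which points to early disease but fixes no share. Purely as an illustration, f = 0.5 gives 31.2% / 18.3% / 7.6%.

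**4. False benefit from IC already present at the start.** This is a different mechanism and arises only if such IC is counted in controls but screened out of the treated group. Here 1 − f is the share of control IC that predates the start. Screened-out patients also leave the treated denominator, so the treated rate is fc/(1 − (1 − f)c). At c = 30%:
- f = 0.9: 0.27/0.97 = 27.8%, false benefit 2.8%.
- f = 0.8: 0.24/0.94 = 25.5%, false benefit 4.7%.

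**5. Power under a common window.** A shorter common window may capture less than 30% control IC. Keeping the planned six-fold reduction (30% to 5%), exact power at 29 against 116 is:

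| Control rate | Treated rate | Power |
|---|---|---|
| 30% | 5% | 87.9% |
| 22.5% | 3.75% | 72.3% |
| 20% | 3.33% | 63.8% |
| 15% | 2.5% | 42.2% |

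**The case against.** The text can be read fairly. Both populations share the day 21-60 ALP criterion, and 12 weeks is the time frame used throughout the aims, so the investigators may well intend one 12-week horizon for both groups. That stands: unequal observation is permitted, not stated. A reader might infer that the plan as worded always watches controls longer; the documents do not support that. Equally, they do not commit to the common reading. The ALP criterion spans 40 days (21 to 60 inclusive) and fixes neither a start nor an end.

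A reader might also infer that treated patients must be IC-free and controls need not be. The exclusion list contains no such rule for either group, so IC already present biases the comparison only if it is handled unequally.

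If IC is mostly early, f is near 1 and the bias is small. At f = 0.9 the total two-sided rejection rate with no drug effect stays below 5% (4.4% / 3.8% / 3.2% at the three control rates), although false benefit alone does rise. If both groups were read to the end of their records, the gap would narrow: by the Study Timeline, a month-0 enrollee has up to 18 months and a month-10 enrollee up to 8 months before analysis ends. This also stands, and it limits the size of the problem.

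Finally, section V admits the small sample and the lack of a randomized control. That admission does not cover unequal observation time, which is avoidable without randomization.

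**Conclusion.** The omission is real: Aim 2 fixes no common day 0 and no common end of IC follow-up, and the planned test cannot repair unequal windows. The direction is conditional. If control records are read without limit, controls are observed longer and an ineffective drug can look protective. If a common 12-week window is used, this bias does not arise.

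The size rests on f, which the documents do not give. For late control IC it is modest if most IC is early: 3.4% / 2.7% / 1.8% at f = 0.9 and 6.5% / 4.5% / 2.6% at f = 0.8, against 1.7% / 1.6% / 1.2% with equal windows. Those figures should not be carried over to IC present at the start, where the denominator also changes and the values at a 30% control rate are 2.8% and 4.7%. All assume 29 and 116 analysed patients and no drug effect.

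Efficacy is a secondary aim of a pilot, so the harm is limited to a possibly misleading go signal for the randomized trial. This is a cheap improvement and leaves the sample-size calculation intact as arithmetic.

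**What to change.** Amend Aim 2 before control IC outcomes are analysed. It cannot be assumed that no control data exist yet: section III says a dataset of over 300 DCD recipients is already being developed to identify the controls.

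1. Set day 0 as first dose for treated patients. For controls, assign a post-transplant day on or after the qualifying ALP, drawn from the treated patients' distribution of start days and without sight of IC outcome.
2. For the Aim 2 comparison, require patients in both groups to be alive, IC-free and otherwise eligible at day 0, and count only first IC diagnoses after it.
3. Apply the same fixed window from day 0 in both groups: 12 weeks, or a longer common window if the timeline allows. For example, 6 months from a month-10 start closes at month 16, before analysis ends at month 18.
4. Restate the expected control rate and the power for that window.

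**Cost.** A few sentences of endpoint wording, two more dates per control (qualifying ALP and first IC; 2 × 116 = 232 dates), and an estimate of the control rate for the chosen window. No visits, procedures or patients are added. Enrolment closes at month 10 and the control cohort is scheduled for months 14-16, so treated start days should be available in time if dosing follows enrolment promptly.

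**Downside.** Controls with IC before day 0 drop out, so fewer than 116 may remain, and stated power falls if the common-window control rate is below 30%, as shown in step 5 of the working.

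### Specific Aim 3 does not require marker samples to precede the IC diagnosis, so week-12 and other post-diagnosis levels can show concurrent association but not early detection

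*Combined protocol and SAP*

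**What the plan says.** The Specific Aims section states the third aim as "To assess the association between serum biomarkers and IC development". Its endpoint relates alkaline phosphatase (ALP), gamma glutamyl transferase (GGT), bile acids, FGF19 and 7AC4 "levels at weeks 0, 4, 8, and 12 of treatment, with development of IC at 12 weeks of treatment".

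Section IV, Analyses, Specific Aim 3 names the method: "We will use the Wilcoxon Rank-Sum test to compare serum ALP" and the other four markers at the same four weeks, "with development of IC at 12 of treatment" (the unit is missing there; weeks is the evident meaning). Neither place says how a sample date must stand to a diagnosis date.

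Section II gives the use the investigators have in mind. They hope to learn whether markers other than ALP "are associated with IC and facilitate early detection", and add that the data may let them explore a predictive score built partly on these markers.

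Section IV defines IC as a finding, "defined as the occurrence of non-anastomotic biliary strictures in the absence of hepatic artery compromise". It fixes no diagnosis date, and the Schedule of Events lists no cholangiography. For GGT, bile acids, FGF19 and 7AC4, that schedule places draws at screening, once in weeks 0-4 ("collect within 3 days after start of treatment"), at week 6, at week 12 and once after treatment. ALP belongs to the weekly routine labs.

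**The concern.** A marker helps early detection only if it is measured before the disease is recognised. The planned comparison splits patients by IC status at week 12 and applies that split to every draw, so samples taken before and after diagnosis enter the same test.

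Post-diagnosis levels can mislead in either direction. Section II describes a cycle in which biliary injury leads to bile acid accumulation, so a high level may be a consequence of IC. The Aim 2 composite endpoint anticipates dilation, stenting, drainage and antimicrobials within the same 12 weeks, and these may already have altered the markers. A late difference could therefore be reported as an early signal, or a real early signal could be diluted by values taken after drainage. With very few cases, one or two such values could decide the result.

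**Working it through.** **1. Lead time at each draw.** Let D be the week of diagnosis and t the week of the draw. Lead time is D − t. A case is a patient with IC by week 12, so D ≤ 12.

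- At t = 12: D − 12 ≤ 0 for every case. No case has positive lead time, whatever the IC rate. This takes IC at 12 weeks to mean diagnosed by then, which is the natural reading. Because no imaging date is fixed, a sample could precede a confirming cholangiogram by days, but that is not useful lead time.
- At t < 12: a case sample has lead time only if D > t. Call the share of such cases f. The documents give no distribution of D and no imaging schedule, so f may lie anywhere from 0 to 1.

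**2. Which draws exist.** Aim 3 lists weeks 0, 4, 8 and 12. The Schedule of Events gives the four non-ALP markers three on-treatment draws: within 3 days of start, week 6 and week 12. For the markers of most interest, week 12 is thus one of three on-treatment draws, and weeks 4 and 8 are not listed at all.

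**3. How many cases.** Aim 3 has no sample size of its own, so the Aim 2 figure is reproduced first. Inputs (Section IV, Analyses, Specific Aim 2): 5% versus 30%, two-sided 0.05, 80% power, 1:4 ratio, 10% dropout.

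- Pooled proportion: (0.05 + 4 × 0.30)/5 = 0.25.
- Uncorrected n = [1.96 × √(1.25 × 0.25 × 0.75) + 0.8416 × √(0.05 × 0.95 + 0.30 × 0.70/4)]² / 0.25² = (0.949 + 0.266)² / 0.0625 = 23.6.
- With continuity correction: (23.6/4) × [1 + √(1 + 2 × 5/(23.6 × 4 × 0.25))]² = 28.4, rounded up to 29 treated, and 4 × 29 = 116 controls.
- Dropout: 29 × 1.1 = 31.9, so 32.

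The stated 32 and 116 reproduce, with 29 evaluable treated patients. Expected IC cases among them:

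- At the planned 5%: 29 × 0.05 = 1.45. P(0 cases) = 0.95²⁹ = 0.226. P(1 case) = 29 × 0.05 × 0.95²⁸ = 0.345. P(0 or 1) = 0.571.
- At 30% (no treatment effect): 29 × 0.30 = 8.7.

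With a single case, the smallest two-sided exact rank-sum p is 2/29 = 0.069. Aim 3 states no significance level, but the 0.05 set for Aim 2 could not be reached.

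**4. Cases left after restriction.** Expected cases with a pre-diagnosis sample at a given draw = 29 × rate × f, where f is an assumption shown over its range:

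| f | 5% rate | 30% rate |
|---|---|---|
| 0 | 0 | 0 |
| 0.25 | 0.36 | 2.2 |
| 0.50 | 0.73 | 4.4 |
| 1 | 1.45 | 8.7 |

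**The case against.** The strongest reply is that Aim 3 is stated as association in the Abstract, in the Specific Aims and again in Section II, where it is a tertiary aim. A week-12 sample can show association, so the formal aim is met. That stands. Early detection and a score are hoped-for uses, and a reader who inferred that the protocol's stated objective is early detection would go too far.

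A reader might also infer that Aim 3 is void, or that about half of all case samples postdate diagnosis. Neither is supported. Draws before week 12 can precede a later diagnosis. The one-half figure needs diagnoses spread evenly over 12 weeks, which nothing in the documents supports, and it uses week-4 and week-8 draws that the schedule does not list for four of the five markers.

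Two limits of the remedy also stand. Restricting to undiagnosed patients removes the effects of diagnosis and treatment but not of undetected disease: no cholangiography is scheduled, and no exclusion criterion names IC already present at enrolment. It also thins an already small number of cases.

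None of this justifies pooling pre- and post-diagnosis samples. Post-diagnosis samples add nothing on early detection, and separating them costs little.

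**Conclusion.** The point holds in limited form. As written, Aim 3 can show concurrent association, but its week-12 comparison, and any earlier sample drawn after diagnosis, cannot support the early-detection or predictive use described in Section II. For week 12 this follows from the case definition, on the reading that a case is IC diagnosed by week 12. For earlier draws the affected share cannot be determined from the documents and may be anything from 0 to 100%.

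The consequence is modest. This is a tertiary aim of a pilot, with about 1.45 expected cases at 5% and 8.7 at 30%, and no trial decision is tied to it. The risk lies in how the results would be read and carried into later work. The mismatch between the Aim 3 draw times and the Schedule of Events is a separate inconsistency that bears on the same analysis.

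**What to change.** In Specific Aim 3, and in the matching paragraph of Section IV, Analyses:

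- Define the IC diagnosis date and take it from the imaging and procedure reports that Section V already says will be reviewed.
- At each draw before week 12, compare levels only among patients not yet diagnosed with IC, by whether IC is diagnosed after that draw and by week 12 (a landmark comparison; the rank-sum test can stay).
- Report week-12 levels and all post-diagnosis samples descriptively, labelled as concurrent association and not as early markers.
- State that not yet diagnosed does not exclude undetected strictures.
- Reconcile the draw times in Aim 3 (weeks 4 and 8) with the Schedule of Events (week 6 for GGT, bile acids, FGF19 and 7AC4).

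The cost is some plan wording and one date field to abstract; the timing rule itself needs no extra draw or visit. The statistical price is fewer cases at later draws, so results will be largely descriptive. Relating week-12 levels to IC diagnosed later is not proposed here: scheduled follow-up ends 4 weeks after treatment and no end date is given for record review, so that would add a new outcome window.
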